- CRV431, 75 mg, softgel capsule, orally QD, in fasted condition
- Placebo, softgel capsule orally QD, in fasted condition

Duration of treatment: Full treatment duration will be defined as 28 days of treatment with CRV431 or placebo.

Criteria for evaluation:

Safety:

Safety and tolerability parameters, including adverse events (AEs), serious adverse events (SAEs), AEs of special interest, physical examinations including weight and height, concomitant medications, laboratory assessments including blood chemistry, hematology and coagulation, urinalysis, pregnancy screening, clinical safety laboratory parameters, ECG, and vital sign assessments, will be determined.

Pharmacokinetics:

Whole blood PK samples will be analyzed for the concentrations of CRV431 along with its major metabolites using a validated liquid chromatography/tandem mass spectroscopy (LC-MS/MS) assay. Subjects will have whole blood PK samples collected at the following time points on Days 1 and 28: 0 hour (pre-dose), 2.0, 4.0 and 8.0 hours (post-dose). A single sample of whole blood will be collected for PK on Day 14 (pre-dose). Standard non-compartmental PK parameters will be calculated from whole blood.

[REDACTED]

[figure not shown]
[REDACTED]	[REDACTED]	[REDACTED]
[REDACTED]	[REDACTED]	[REDACTED]
[REDACTED]	[REDACTED]	[REDACTED]
[REDACTED]	[REDACTED]	[REDACTED]
[REDACTED]	[REDACTED]	[REDACTED]

[REDACTED]

Statistical methods:

The sample size is not based on statistical considerations. It is expected that the number of subjects per cohort, 12 subjects in Cohort A, 6 subjects in Cohort B, 12 subjects in Cohort C and 6 subjects in Cohort D is enough to assess the safety, tolerability, and PK of CRV431, as well as providing a preliminary indication of its antifibrotic activity, based on biomarkers, for Phase 2B study planning purposes. To evaluate drug effect and dose response, comparisons of Cohorts will include Cohort A versus Cohort B, Cohort C versus Cohort D and Cohort A versus Cohort C.

Data will be listed by subject and summarized using descriptive statistics.

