4. LIST OF ABBREVIATIONS AND DEFINITIONS

Abbreviations/Acronyms	Definition
AE(s)	Adverse event(s)
ALT	Alanine aminotransferase
AST	Aspartate aminotransferase
AUC	Area under the concentration time curve
AUC ₀₋₂₄	Area under the concentration time curve from time 0 to the 24-hour time point
AUC ₀₋₄₈	Area under the concentration time curve from time 0 to the 48-hour time point
AUC _{0-last}	Area under the concentration time curve calculated from 0 to the last observed concentration
AUC _{0-inf}	Area under the concentration time curve from 0 to infinity
AUC _{0-t}	Area under the concentration time curve from time zero to time t
%AUC _{t_{expol}}	Percentage of AUC _{0-inf} extrapolated beyond T _{last}
CL/F	Apparent total oral clearance (parent compound only)
C _{max}	Maximum observed whole blood concentration
C _{min}	Minimum observed whole blood concentration
DSMB	Data Safety Monitoring Board
ECG	Electrocardiogram
IEC	Independent Ethics Committee
IRB	Institutional Review Board
NAFLD	Nonalcoholic fatty liver disease
f _u	Fraction Unbound
PK	Pharmacokinetics
PK/PD	Pharmacokinetics/Pharmacodynamics
QD	Once daily
QTcF	Friderica's QT Correction Formula
SAE(s)	Serious adverse event(s)
V _z /F	Apparent volume of distribution during the terminal elimination phase

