12.3.2. Analysis of Covariance

Placebo subjects will be used for comparison with all presumed NASH treatment subjects using the following analysis.

An analysis of covariance (ANCOVA) will be performed on the ln-transformed AUC_{0-inf} and C_{max} . The ANCOVA model will contain a categorical factor of population (for subjects with F2/F3 presumed NASH, and F2/F3 presumed NASH placebo subjects), a categorical covariate (sex), and continuous covariates (age, weight, BMI and ideal body weight).

The comparisons of interests are:

- CRV431-treated F2 presumed NASH subjects versus placebo treated F2 presumed NASH subjects stratified by dosing cohort, i.e. Cohort A (75 mg QD) versus Cohort C (225 mg QD);
- CRV431-treated F3 presumed NASH subjects versus placebo treated F3 presumed NASH subjects stratified by dosing cohort, i.e. Cohort A (75 mg QD) versus Cohort C (225 mg QD);
- CRV431-treated pooled F2/F3 presumed NASH subjects versus pooled placebo treated F2/F3 presumed NASH subjects stratified by dosing cohort will only be evaluated for differences [REDACTED]

A full covariate population PK/PD model will be developed for exploratory purposes.

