12.3.3. Ratios and Confidence Intervals

Ratios of least-squares means (LSM) will be calculated using the exponentiation of the difference between F2/F3 presumed NASH groups LSM from the analyses on the ln-transformed

AUC_{0-inf} and C_{max} . These ratios will be expressed as a percentage relative to the F2/F3 presumed NASH placebo control group.

Ninety percent (90%) confidence intervals (CIs) for the ratios will be derived by exponentiation of the CIs obtained for the difference between F2/F3 presumed NASH groups LSM resulting from the analyses on the ln-transformed AUC_{0-inf} and C_{max} . The CIs will be expressed as a percentage relative to the F2/F3 presumed NASH placebo control group.

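### AUC0-inf is a named ANCOVA and ratio variable, but post-dose sampling stops at 8 h; at the protocol's own 75 mg means at least 56% of even AUC0-24 lies after the last sample

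*Combined protocol and SAP*

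**What the plan says.** Protocol 12.3.2 specifies an ANCOVA that "will be performed on the ln-transformed AUC_{0-inf} and C_{max"}. Protocol 12.3.3 derives least-squares-mean ratios and 90% confidence intervals from it, and states: "These ratios will be expressed as a percentage relative to the F2/F3 presumed NASH placebo control group". Neither section names the day.

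The synopsis sets whole-blood sampling at "time points on Days 1 and 28: 0 hour (pre-dose), 2.0, 4.0 and 8.0 hours (post-dose"), and Table 6 agrees. The only other scheduled PK sample is Day 14 pre-dose; Table 3 adds one only at early termination. On method the synopsis says: "Standard non-compartmental PK parameters will be calculated from whole blood". A population PK/PD model is also planned (6.4.2, 12.3.2, 12.3.4). Section 12.3.2 calls it exploratory, and it is not named as the source of the AUC0-inf in the ANCOVA.

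The abbreviation list defines AUC0-24 ("Area under the concentration time curve from time 0 to the 24-hour time point"), AUC0-48 ("Area under the concentration time curve from time 0 to the 48-hour time point") and the percentage of AUC0-inf "extrapolated beyond T"last. Table 6 has no 48 h sample, so a term in that list does not show that the parameter is planned. Table 5, protocol 12.3 and SAP 6.2 are redacted. No readable SAP text names AUC0-inf, and SAP Appendix B lists no PK table.

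**The concern.** AUC0-inf is a usable exposure measure when sampling covers most of the curve and the terminal slope can be estimated. Here sampling stops one third of the way through a 24 h dosing interval, and the protocol's own figures describe a drug whose level has barely fallen by then. The slope would rest on at most three points, some of them possibly before or near the peak. On Day 28, AUC0-inf would also include drug carried over from the 27 earlier doses, so it would not measure the exposure from one dose.

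Pharmacokinetics is a primary objective, and this is the only inferential PK analysis in the readable text. As written, its ratio and interval for total exposure would mainly reflect extrapolation. Cmax, trough and the population model are not affected by this problem.

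**Working it through.** The plan states no extrapolation figure to reproduce. The check asks how much of the area must lie after 8 h.

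**Inputs.** Protocol 5.3, 75 mg once daily for 28 days: Cmax 1397.5 ± 97.8 and mean trough 889.5 ± 70.4 ng/mL. Single 75 mg dose: Cmax 334 ± 106. At 225 mg: steady-state Cmax 1844 ± 321.9, no trough. The ± values are unlabelled. Last sample: 8 h. Dosing interval: 24 h.

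**Day 28 bound, no kinetic model.** Within one steady-state interval the level never exceeds Cmax or falls below trough.
- Trough/peak = 889.5/1397.5 = 0.64.
- AUC0-8 ≤ 8 × 1397.5 = 11,180 ng·h/mL.
- AUC8-24 ≥ 16 × 889.5 = 14,232 ng·h/mL.
- Share of AUC0-24 after 8 h ≥ 14,232/(14,232 + 11,180) = 14,232/25,412 = 56.0%.
- Both means shifted adversely by one ± unit (1495.3 and 819.1): 8 × 1495.3 = 11,962; 16 × 819.1 = 13,106; 13,106/25,068 = 52.3%.
- Upper limit at the means: 16 × 1397.5 = 22,360; 8 × 889.5 = 7,116; 22,360/29,476 = 75.9%.

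AUC0-inf adds the area beyond 24 h, all of it after the last sample, so its unsampled share exceeds that of AUC0-24.

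**How much larger: illustration only.** Assume a peak at 2 h, a linear rise from trough before it and log-linear decline after it.
- k = ln(1397.5/889.5)/22 = 0.02054 per h (half-life about 34 h).
- Level at 8 h = 1397.5 × exp(−6k) = 1,235.5 ng/mL.
- AUC0-8 = 2,287 (rise) + 7,889 (decline) = 10,176; AUC8-inf = 1,235.5/k = 60,164 ng·h/mL.
- Share after 8 h = 60,164/70,340 = 86%.

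Oral one-compartment models fitted to the same peak and trough, with assumed Tmax 1 to 6 h, give 82% to 85% (half-life 22 to 35 h). Fitting the accumulation ratio 1397.5/334 = 4.18 instead gives about 91% to 92% (half-life 57 to 61 h). The two routes disagree, so the range indicates scale only: roughly 80% to 90%.

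**Day 1, conditional.** Under linear superposition, Day 1 AUC0-inf equals steady-state AUC0-24, which is at least 24 × 889.5 = 21,348. AUC0-8 is at most 8 × 334 = 2,672. The share after 8 h would be at least 1 − 2,672/21,348 = 87%. Two figures strain the assumption: accumulation is 4.18, against about 2.1 to 2.7 implied by peak and trough, and three times the dose gives 1844/1397.5 = 1.32 times the Cmax. If, say, Day 1 AUC0-inf were half as large (10,674), the share would be 1 − 2,672/10,674 = 75%.

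**Replacement: interpolation error.** With the Day 28 pre-dose level as the 24 h value, the trapezoid over 8 to 24 h is 16 × (C8 + C24)/2. If levels do not rise after 8 h, the true area lies between 16 × C24 and 16 × C8. The error is then at most 8 × (C8 − C24) ≤ 8 × (1397.5 − 889.5) = 4,064 ng·h/mL, and 4,064/21,348 = 19%. With the adverse shifts it is 8 × (1495.3 − 819.1) = 5,410; 5,410/19,658 = 28%.

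**The case against.** **The contrasts fail anyway.** Placebo subjects have no CRV431 exposure, so ln AUC0-inf is undefined in the reference group. This is true, and it is why the two repairs belong together. Changing the reference alone would still leave AUC0-inf mostly unobserved.

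**Redacted text may already deal with it.** An extrapolation limit or a planned AUC0-24 may exist, so no missing rule is alleged. A limit would not turn unsampled area into observed area; on the 75 mg Day 28 mean profile, a limit below 56% would exclude the value. The readable sections still name AUC0-inf.

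**The 56% applies equally to the proposed replacement.** Correct. It is a share of AUC0-24, and AUC0-24 is what would be reported instead. The case for the replacement is that its unsampled part is bounded under stated assumptions, while the tail of AUC0-inf is not.

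**Stronger readings that a reader might infer.** The documents do not support these:
- That the protocol plans no kinetic model. It plans an exploratory population PK/PD analysis; the point is only that the 56% bound needs no model.
- That at least 87% of Day 1 AUC0-inf is unsampled. That needs linear, time-invariant kinetics, which the protocol's own figures strain.
- That the same share holds at 225 mg. With no trough given, nothing can be computed for those 12 of the 24 active subjects.
- That dose escalation or stopping is compromised. No visible decision of either kind uses AUC0-inf.

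**Conclusion.** The point holds as a mismatch, in readable text, between a named analysis variable and the sampling schedule. At the 75 mg means at least 56% of steady-state AUC0-24 lies after the last sample (52% with adverse shifts), and the share of Day 28 AUC0-inf is larger, roughly 80% to 90% under illustrative models. The bound describes a mean profile, not every subject. It assumes steady state and that the protocol 5.3 figures carry over to this population, although protocol 5.4 calls this the first study in presumed NASH F2/F3.

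The mismatch is certain; its size is known only at 75 mg. It should be fixed because it touches a primary objective and costs little, but the damage stays within the AUC0-inf ANCOVA, ratios and intervals.

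**What to change.** In protocol 12.3.2 and 12.3.3, and in the SAP if the analysis is carried there:
1. State the day analysed.
2. Replace AUC0-inf with Day 28 steady-state AUC0-24, taking the Day 28 pre-dose level as the 24 h value, alongside Cmax.
3. Replace the placebo reference for exposure ratios with Cohort A versus Cohort C. The synopsis already lists "Cohort A versus Cohort B, Cohort C versus Cohort D and Cohort A versus Cohort C". The ratio then answers a question about dose.
4. If AUC0-inf is reported at all, give it descriptively with its extrapolated percentage.
5. Check the result against the redacted Table 5, protocol 12.3 and SAP 6.2.

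**Cost.** Wording only; no new sample, visit or subject.

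**Downside.** Between 56% and 76% of AUC0-24 (the model-free range at the 75 mg means) is still interpolated, from the 8 h sample to a 24 h value that is substituted, not measured. The substitution assumes steady state. The pre-dose level also follows a dose normally taken at home the day before, with compliance checked by subject report and pill count and a 30-minute post-dose fast, against 2 hours on Day 28. Subjects with missed, mistimed or changed doses shortly before Day 28 should be flagged. If levels do not rise after 8 h and the substitution holds, the error is limited to about 19% of AUC0-24 at the 75 mg means.

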12.3.3. Ratios and Confidence Intervals

Ratios of least-squares means (LSM) will be calculated using the exponentiation of the difference between F2/F3 presumed NASH groups LSM from the analyses on the ln-transformed

AUC_{0-inf} and C_{max} . These ratios will be expressed as a percentage relative to the F2/F3 presumed NASH placebo control group.

Ninety percent (90%) confidence intervals (CIs) for the ratios will be derived by exponentiation of the CIs obtained for the difference between F2/F3 presumed NASH groups LSM resulting from the analyses on the ln-transformed AUC_{0-inf} and C_{max} . The CIs will be expressed as a percentage relative to the F2/F3 presumed NASH placebo control group.

12.3.4. Pharmacokinetics Analyses

Values will be calculated for the whole blood concentrations and the PK parameters listed in Section 10.4, using appropriate summary statistics to be fully outlined in the SAP. Population PK/PD analysis will be used to explore PK dependent covariates and quantitative concentration-effect relationships.

12.3.5. Safety Analyses

All safety data will be populated in the individual CRFs. All safety data will be listed by subjects.

Adverse events will be coded using the most current version of Medical Dictionary for Regulatory Activities (MedDRA) summarized by treatment for the number of subjects reporting the treatment emergent adverse event (TEAE) and the number of TEAEs reported. A by-subject AE data listing including verbatim term, coded term, treatment, severity, and relationship to population will be provided.

Safety data including ECGs, vital signs assessments and clinical laboratory results, will be summarized by population and point of time of collection.

Descriptive statistics using appropriate summary statistics will be calculated for quantitative safety data as well as for the difference to baseline, when appropriate. In addition, a shift table describing out of normal range shifts will be provided for clinical laboratory results.

Concomitant medications will be listed by subject and coded using the most current version of WHO drug dictionary. Medical history will be listed by subject.

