7.7. Safety Criteria for Adjustment or Stopping Doses

7.7.1. Individual Subject Criteria

If any of the criteria below are met by an individual subject, then no further dosing will occur at any of the study sites until a review of all available safety information is performed by the DSMB, Medical Monitor, and Sponsor. Appropriate Regulatory Agencies and Ethics Committees will be informed as applicable. If it is later determined that further dosing can be performed safely then an application for a substantial protocol amendment will be submitted to the appropriate Regulatory Agencies and Ethics Committees, if applicable. Stopping criteria for an individual subject includes:

- Grade 3 or higher CTCAE AEs possibly or probably related to study drug as determined by the investigator and sponsor;
- Grade 4 CTCAE AEs regardless of relation to study drug as determined by the investigator and sponsor;
- Any SAEs thought to be related to the study drug as determined by the investigator and sponsor.

For subjects experiencing any hepatic AEs or SAEs judged by the investigator or sponsor to be related to study drug, the investigator, DSMB, Medical Monitor and Sponsor will review all available safety data and make a determination to proceed with one of the following options:

- If the event was a drug-induced liver injury (DILI), considered as increases in aminotransferases (AT) $>3 \times$ ULN or $>3 \times$ baseline where baseline is defined as the average values of Screening and Day -1, no additional subjects will be dosed until it is determined that it is safe to proceed and in addition the frequency of blood chemistries will increase to daily, if appropriate.

- Repeat testing of ALT, AST, ALP, TBL will be performed within 48-72 hours to confirm the abnormality.
- If there are persistent elevations of AT > 3 x ULN or a 2-fold increase above baseline values (for those subjects with elevated values prior to drug exposure) upon repeat testing then close observation visits should be implemented and/or discontinuation of drug should be considered. Close Observations are described in Section 7.8.
- If the event was not a DILI, as defined above, one of the following actions will be taken:
 - Dose an entire additional cohort at the same or lower dose than the dose taken by the subject that experienced the event in question;
 - Continue to pause the study, until it is determined, that it is safe to proceed.

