4. GENERAL CONSIDERATIONS FOR DATA ANALYSIS

Unless otherwise specified, continuous variables will be summarized by presenting the number of non-missing observations, mean, standard deviation, median, minimum, and maximum. Categorical variables will be summarized by presenting the number of subjects and percentages for each category.

All mean and median values will be formatted to one more decimal place than the measured value. Standard deviation values will be formatted to two more decimal places than the measured value. Minimum and maximum will be formatted to the same number of decimal places as the measured value.

Analyses will be performed using SAS for Windows statistical software, version 9.4 or higher (SAS, Cary, NC), except where other software may be deemed more appropriate.

[REDACTED]

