4.3 Assessment Windows

For the purpose of listing and summarizing data, the time-in-study for each subject observation will be defined using study days as defined in the Schedule of Events (Appendix A). No analysis windows are planned for the study regarding data collected outside the protocol specified windows. All data will be included in the analysis based on the visit as it is recorded in the database.

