7.3 Clinical Laboratory Assessments

Hematology, Coagulation, Blood Chemistry and Urinalysis data will be summarized by treatment group and visit. All clinical laboratory data will be converted to International System of Units (SI). Both raw and change from baseline values will be summarized by presenting the descriptive statistics by treatment group and visit.

Central and local drug and alcohol test results and pregnancy tests results will be listed.

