12.2 Appendix B: List of Proposed Tables

Summary of Subject Disposition – All Subjects

Summary of Protocol Deviations – Safety Set

Summary of Demographics – Safety Set

Summary of Medical History by System Organ Class and Preferred Term – Safety Set

Summary of Prior and Concomitant Medications – Safety Set

Summary of Non-drug Therapies by System Organ Class and Preferred Term – Safety Set

Summary of Biomarkers: Change from Baseline – Safety Set

Summary of Biomarkers: Percent Change from Baseline – Safety Set

Summary of Exposure – Safety Set

Overall Summary of Treatment-emergent Adverse Events – Safety Set

Treatment-emergent Adverse Events by System Organ Class and Preferred Term – Safety Set

Treatment-emergent Adverse Events by System Organ Class, Preferred Term and Highest Severity – Safety Set

Treatment-emergent Adverse Events by System Organ Class, Preferred Term and Strongest Relationship to Study Drug – Safety Set

Treatment-emergent Serious Adverse Events by System Organ Class and Preferred Term – Safety Set

Treatment-emergent Adverse Events Leading to Study Withdrawal by System Organ Class and Preferred Term – Safety Set

Summary of Blood Chemistry Results – Safety Set

Summary of Hematology Results – Safety Set

Summary of Urinalysis Results – Safety Set

Summary of Vital Signs – Safety Set

Summary of ECG – Safety Set

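### SAP 7.3 and Appendix B omit the protocol's laboratory shift table, and no planned laboratory or ECG table counts subjects who cross a limit

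*Combined protocol and SAP*

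**What the plan says.** Protocol 12.3.5 lists several safety outputs: descriptive statistics, differences from baseline where appropriate, listings ("All safety data will be listed by subjects") and, as an addition, the commitment that "a shift table describing out of normal range shifts will be provided for clinical laboratory results".

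SAP 7.3 covers the laboratory data in two statements: "Hematology, Coagulation, Blood Chemistry and Urinalysis data will be summarized by treatment group and visit" and "Both raw and change from baseline values will be summarized by presenting the descriptive statistics by treatment group and visit". SAP section 4 defines the continuous summary as the "number of non-missing observations, mean, standard deviation, median, minimum, and maximum". SAP 7.5 treats ECG intervals, including QTcF, in the same descriptive way.

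Appendix B of the SAP proposes three laboratory tables: blood chemistry, urinalysis and "Summary of Hematology Results – Safety Set". It lists no shift table, no threshold table and no title that mentions coagulation.

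For timing, SAP 4.3 says "All data will be included in the analysis based on the visit as it is recorded in the database". The protocol generates results outside the visit schedule. Section 7.7.1 says "Repeat testing of ALT, AST, ALP, TBL will be performed within 48-72 hours to confirm the abnormality", and section 7.8 adds liver tests two or three times a week under close observation.

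**The concern.** Safety and tolerability against placebo is a primary objective, with 12 active and 6 placebo subjects per dose level. In groups of that size a hepatic or QTc signal is likely to be one or two people, not a shift in the centre of the distribution.

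The protocol's own limits are built that way. Section 7.7.2 acts on at least one subject with a confirmed, drug-related aminotransferase rise, and on at least three subjects with related Grade 3 or 4 laboratory abnormalities or confirmed QTcF excursions. Sections 7.7.1 and 8.3.1 include criteria that need two findings in the same subject. A report produced strictly from the SAP would lack the one subject-level laboratory table that the protocol promised, and its laboratory and ECG tables would not say how many subjects in each group passed those limits.

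**Working it through.** The documents state no figure on this point, so there is nothing to reproduce. The check compares the texts and adds one labelled illustration.

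**1. Promised against planned.**

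| Output | Promised in | SAP 7.3 / 7.5 | SAP Appendix B |
|---|---|---|---|
| Laboratory descriptive statistics | Protocol 12.3.5 | Yes | Chemistry, hematology, urinalysis |
| Laboratory shift table | Protocol 12.3.5 | No | No |
| Coagulation summary | SAP 7.3 | Yes | No title names it |
| Counts of subjects beyond a limit | Not promised | No | No |

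Parts of the SAP are redacted (within sections 4 and 4.1, and sections 6.2, 6.3, 9 and 10). Sections 7.3 and 7.5 and Appendix B, where these outputs belong, show no redaction.

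**2. What by-visit statistics can show.** Inputs: n = 12 (Protocol 12.1); the 3 x ULN limit (Protocol 7.7.2). Assumption, not from the documents: every subject starts at ALT b = 1.0 x ULN and k subjects rise to f x ULN at one visit. Mean = [(n − k)b + kf]/n.

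- k = 1, f = 3.01: (11 + 3.01)/12 = 1.17; mean change +0.17; median 1.0; maximum 3.01.
- k = 3, f = 3.01: (9 + 9.03)/12 = 1.50; mean change +0.50; median 1.0; maximum 3.01.
- k = 2, f = 3.01: (10 + 6.02)/12 = 1.335. This is practically the mean for k = 1, f = 5, which is (11 + 5)/12 = 1.333.

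So the maximum shows that someone crossed but not how many. The mean does move with k, but cannot be turned back into a count. With b = 1.5 the pattern holds: for k = 1 and k = 3 at f = 3.01 the mean changes are (3.01 − 1.5)/12 = +0.13 and 3(3.01 − 1.5)/12 = +0.38, with median 1.5 and maximum 3.01 in both. In a placebo group of 6 with b = 1.0, one and two subjects at 3.01 again share median 1.0 and maximum 3.01. A shift or threshold table would print k/n directly.

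**3. Joint findings.** Protocol 8.3.1 pairs ALT with bilirubin. Protocol 7.7.1 pairs ALT/AST with bilirubin or INR for subjects whose baseline is at least 5 x ULN. A maximum for each analyte separately cannot show whether the two maxima belong to one subject.

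**4. Repeat results.** Under SAP 4.3 a 48-72 hour repeat follows its database label. If it is labelled unscheduled, it has no column in the Schedule of Events. If it carries a scheduled visit's label, that subject has two values there and no rule selects one.

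**5. Baseline.** Protocol 7.7.1 defines baseline for the drug-induced liver injury criterion as the average of Screening (S) and Day -1 (D). SAP 4.6 uses the last pre-dose value (L). The limits at three times baseline are 3(S + D)/2 and 3L. They differ by 1.5(S + D − 2L), so they agree only when L equals that average. Chemistry is also scheduled on Day 1, and Protocol 11.1.6.2 has samples drawn before dosing, so L will often be a value that the average does not use.

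**The case against.** The best defence is that little is lost. SAP section 4 includes minimum and maximum, so one large excursion at a recorded visit is printed. Laboratory changes that need an intervention are reported as adverse events (Protocol 11.4), graded by CTCAE and tabulated by highest severity (SAP 7.2.5). Subjects who meet the withdrawal criteria must discontinue, and reasons for discontinuation are tabulated (SAP 5.1). All safety data are listed, and 36 subjects can be read one by one. The SAP is silent on shift tables and does not revoke them. Appendix B is only a proposed list, and Protocol 11.1.6.1 places PT/INR in a combined hematology and coagulation panel, so the hematology table may hold it. The protocol promises no threshold counts and no ECG shift table.

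Most of this stands, and it limits the point. Values are retained and visible somewhere. PT/INR is a question of where it is tabulated, and the INR criterion reaches only subjects with high baseline enzymes. Threshold counts are a recommended addition and not a broken promise.

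It does not answer the core. The SAP describes itself as the detailed account of the protocol's methods, and where it specifies the laboratory outputs the promised table is missing. A listing is not a count by treatment group. The adverse-event route depends on a judgement of clinical significance by an investigator who, under Protocol 7.3.3, knows the treatment; a shift table does not.

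**Conclusion.** The point holds in a limited form. A promised primary-safety output is absent from the SAP, and the by-visit method set out there cannot supply subject counts or joint findings. In the illustration, 1/12 and 3/12 subjects beyond 3 x ULN share the same median and maximum. That rests on an assumed common baseline and shows the mechanism, not an expected result.

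A reader might infer more, and the documents do not support it:

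- That the SAP reports means alone. It also gives the median, minimum and maximum.
- That liver signals reach no summary. The maximum and the adverse-event tables can show them, and listings remain.
- That confirmatory repeats are excluded. SAP 4.3 says all data are included; what is missing is a rule for assigning them.
- That early-termination results are unscheduled. Early termination has its own column in the Schedule of Events.
- That coagulation goes unanalysed. SAP 7.3 commits to summarising it.

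The SAP should be corrected before database lock. The data themselves are not at risk.

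**What to change.** In SAP 7.3, 7.5 and Appendix B:

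1. Restore the laboratory shift table by treatment group, as baseline category against worst post-baseline category, using every post-dose value including repeat, unscheduled and early-termination results. State in SAP 4.3 how such results enter the by-visit tables.
2. Add counts of subjects, by treatment group, who cross the aminotransferase, bilirubin, INR and QTcF limits as the protocol already states them, with joint criteria assessed within subject. Reconcile the baseline definitions in Protocol 7.7.1 and SAP 4.6 for these counts, and say which one each count uses.
3. State that PT/INR is tabulated, either in the hematology table (retitled to say so) or in a table of its own.

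The cost is a few extra tables and some programming from data already collected. No clinical rule, visit or sample changes.
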